6.3 SUBJECTS SETS ANALYSED

- Randomised set:
This subject set includes all randomised subjects, whether treated or not.
- Treated set (TS):
This subject set includes all subjects who were documented to have been administered at least one dose of investigational treatment.
- Pharmacokinetic set (PKS):
This subject set includes all subjects in the treated set who provide at least one evaluable observation for at least one PK endpoint without important protocol violations relevant to the evaluation of PK.

Table 6.3: 1 Subject sets analysed

Class of endpoint	Subject set	
	Treated set	Pharmacokinetics set
Primary endpoint	X	
(other) Secondary and further endpoints	X	X
Safety endpoints	X	
Demographic/baseline endpoints	X	
Pharmacokinetics analysis		X

In addition, the population group is defined as Alzheimer's Dementia group, schizophrenia group and healthy volunteer group. The ophthalmological assessment will be done by population group.

6.5 POOLING OF CENTRES

This section is not applicable.

6.6 HANDLING OF MISSING DATA AND OUTLIERS

With respect to safety evaluations, it is not planned to impute missing values other than AE start dates and times. Missing or incomplete AE dates are imputed according to BI standards (see “Handling of missing and incomplete AE dates”). (1)

For handling of missing data in PK evaluation, refer to CTP Appendix Section 10.1.2 and 029-DCP-102. (2)

6.7 BASELINE, TIME WINDOWS AND CALCULATED VISITS

Unless otherwise specified, the baseline is the last available measurement before the first trial medication intake. For laboratory data that were repeatedly measured, baseline is defined to be the last available measurement before the first trial medication intake.

7. PLANNED ANALYSIS

No statistical hypothesis testing is planned. Variables will be evaluated by descriptive statistical methods in this trial.

For End-Of-Text (EoT) tables, the set of summary statistics is: N / Mean / SD / Min / Median / Max.

For displays that are provided for endpoints with some extreme data, median, quartiles and percentiles should be preferred to mean, standard deviation, minimum and maximum

Tabulations of frequencies for categorical data will include all possible categories and will display the number of observations in a category as well as the percentage (%) relative to the respective treatment group (unless otherwise specified, all subjects in the respective subject set whether they have non-missing values or not). Percentages will be rounded to one decimal place. The category missing will be displayed only if there are actually missing values.

7.1 DEMOGRAPHIC AND OTHER BASELINE CHARACTERISTICS

Only descriptive statistics are planned for this section of the report, based on the TS. The following variables will be displayed: gender, age, race, ethnicity, height, weight, body mass index, smoking and alcohol status.

7.2 CONCOMITANT DISEASES AND MEDICATION

Only descriptive statistics are planned for this section of the report. The concomitant disease will be summarized by MedDRA primary system organ class and preferred term. The concomitant medications taken at baseline and those while on treatment will be coded using the WHO Drug coding dictionary. Concomitant medications will be summarized by WHO Drug ATC coding.

7.3 TREATMENT COMPLIANCE

On each treatment day, study drug is administered to the subject at the study centre or at the ophthalmology site. Date and time of study drug intake is documented on day 1-14 of the treatment interval.

7.4 PRIMARY ENDPOINT

Ocular adverse events will be those events coded to the SOC 'Eye disorders' determined by the investigator at end of trial. The assessment of ocular adverse events will be done on treated set. Ocular adverse events analyses will be performed in accordance with BI standards, essentially, tabulations of frequencies will be displayed. Refer to [Section 7.8.1](#) for a description of the analysis of adverse events.

7.5 SECONDARY AND FURTHER ENDPOINTS

7.5.1 Key secondary endpoints

This section is not applicable as no key secondary endpoint has been specified in the protocol.

7.5.2 (Other) Secondary endpoints

Summary of drug-related AEs as determined by the investigator at end of trial will be performed in accordance with BI standards, essentially, tabulations of frequencies will be displayed. Refer to [Section 7.8.1](#) for a description of the analysis of adverse events.

The analysis of standard PK parameters, $C_{max,ss}$ and $t_{max,ss}$, will be performed as described in CTP Section 7.3.5 and also according to 029-DCG-103 ([3](#)). Descriptive analyses are planned.

7.7 EXTENT OF EXPOSURE

Extent of exposure will be summarized by treatment group using descriptive statistics for days of exposure as well as number (percent) of patients whose total exposure falls in the following categories:

1 day, 2 days, 3 days, 4 days, etc. until 14 days, and ≥ 15 days

Exposure to treatment will be calculated as study drug stop date minus study drug start date plus 1. Total exposure will summarize exposure to both doses.

7.8 SAFETY ANALYSIS

All safety analyses will be performed on the treated set.

7.8.1 Adverse events

The analyses of adverse events (AEs) will be descriptive in nature. All analyses of AEs will be based on the number of subjects with AEs and NOT on the number of AEs. AEs will be coded using the Medical Dictionary for Drug Regulatory Affairs (MedDRA).

For analysis, multiple AE occurrence data on the CRF will be collapsed into an AE provided that all of the following applies:

- All AE attributes are identical (LLT, intensity, action taken, therapy required, seriousness, reason for seriousness, relationship, outcome, AE of special interest).
- The occurrences were time-overlapping or time-adjacent (time-adjacency of 2 occurrences is given if the second occurrence started ≤ 24 hours from the end of the first occurrence).

For further details on summarization of AE data, please refer to the guideline 'Handling and summarization of adverse event data for clinical trial reports and integrated summaries' ([4](#)) [001-MCG-156].

The relationship of an AE to the study drugs treatments will be assessed by the investigator.

The analysis of AEs will be based on the concept of treatment-emergent AEs. That means that all AEs occurring between first study drug intake till 7 days (inclusive) after last study drug intake will be considered "treatment-emergent" and be assigned to the randomised treatment.. AEs occurring before first study drug intake will be assigned to 'screening' or 'baseline'; AEs occurring after last study drug intake + 7 days till end-of-trial visit will be assigned to 'post-treatment' (for listings only). AEs occurring after the end-of-trial visit will be assigned to 'post-study' (for listings only). For details on the treatment definition, see [Section 6.1](#).

According to ICH E3 ([5](#)), AEs classified as 'other significant' needs to be reported and will include those non-serious and non-significant adverse events with

- (i) 'action taken = discontinuation' or 'action taken = reduced', or
- (ii) marked haematological and other lab abnormalities or lead to significant concomitant therapy as identified by the Clinical Monitor/Investigator at a Medical Quality Review Meeting.

Overall summaries of adverse events will be presented to summarise any AEs, severe AEs, drug-related AEs, AEs leading to treatment discontinuation, serious AEs, drug-related serious AEs, and AEs leading to death.

The frequency of subjects with adverse events will be summarised by treatment, primary system organ class and preferred term. Separate tables will be provided for subjects with other significant adverse events according to ICH E3 ([5](#)), for subjects with adverse events of special interest (AESI) and for subjects with serious adverse events. The AESI are described in Section 5.2.2.1 of the CTP. There is a field on the eCRF for the site to designate that an AE is an AESI. This variable will be used to identify the AESI.

The system organ classes will be sorted alphabetically, preferred terms will be sorted by frequency (within system organ class).

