4.1.2 Method of assigning subjects to treatment groups

Subjects eligible for the trial will be assigned at random in a 1:1 ratio of 25 and 100 mg dose per group at Visit 2 (cf. Section 3.1). Details on randomization are provided in Section 7.5. Assignment to the treatment groups will be determined at the site by having the next lowest sequentially numbered medication kit within each subject population group assigned (AD group, CIAS group, HV/AD low age group, HV/AD high age group, HV/CIAS low age group, HV/CIAS high age group). The assigned medication number will be entered in the eCRF and the corresponding medication kit should be given to the patient/healthy volunteer.

Using this procedure, the Investigator and study staff will be blinded to the assignment to which the patient was randomized. Note that the medication numbers assigned to the patient are different from the patient number.

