7.6 DETERMINATION OF SAMPLE SIZE

It is planned to include a total of 60 subjects in this study: 20 healthy volunteers; 20 patients with Alzheimer's disease and 20 patients diagnosed with schizophrenia. The planned sample size is not based on a power calculation nor on statistical consideration. The size of 10 subjects per population and per dose group is in general considered as sufficient for the exploratory evaluation of multiple dose ophthalmologic assessment, safety and pharmacokinetics.

Doc. No.: c02218444-07 Trial Protocol Revision 3 Page 65 of 101

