6.2 IMPORTANT PROTOCOL VIOLATIONS

The following table defines the different categories of important protocol violations (IPVs). The final column describes which IPVs will be used to exclude subjects from the different subject analysis sets.

Table 6.2: 1 Important protocol violations

Category/Code	Description	Example/Comment	Potentially excluded from
A	Entrance criteria not met		
A1	Inclusion criteria not met		
A1.1	Diagnoses of schizophrenia not established	IPV if any of the clinical features defining the population (IN1) are not met.	None
A1.2	Diagnosis of AD not established	IPV if any of the clinical features defining the population (IN1) are not met	None
A2	Exclusion criteria met		
A2.1	Presence of active ocular conditions	Any of EX1-EX4 are met.	None
A2.2	Suicidal ideation or behavior	Any of EX13-EX14	None
A2.3	Other clinically relevant baseline conditions	Any of EX12, 15, 17-22, 24-26, 28	None
B	Informed consent		
B1	Informed consent not available/not done	Informed consent date missing; no signature on ICF	All
B2	Informed consent too late	Informed consent date <actual consent date> was after Visit 1 date <Visit 1 date>	None
C	Trial medication and randomisation		
C1	Incorrect trial medication kit assigned	Medication (kit) number assigned is not from the correct group (AD, CIAS etc.). OR Medication number was not assigned in sequential order (as subjects were randomized).	None
C2	Incorrect trial medication administered		
C2.1	Incorrect trial medication administered on any of days 2-13.	Trial medication administered on any of days 2-13 was not from the medication kit assigned to subject.	None
C2.2	Incorrect trial medication administered on PK day 1 or 14.	Subject was administered medication from kit assigned to another subject on days 1 or 14 (PK visit)	PKS
C3	Medication code broken inappropriately	Medication code broken inappropriately - reason for medication code break <reason>	None
D	Concomitant medication		
D1	Prohibited medication use 3 days prior to Day 1 and/or Day 14.	Use of St. Johns wort, Carbamazepine, extracts from Gingko, artemisinin, enzalutamide, efavirenz, lopinavir, ritonavir, tipranavir, & rifampicin.	None
F	Incorrect timing		
F1	Peak exposure visual procedures performed outside time range.	Visual procedures were not completed during estimated peak exposure time range (between Day 5 and Day 10 (except Day 7), 20-90 minutes after dosing).	None
Z	Other		
Z3	Other protocol violations affecting safety only		None

PKS: PK set

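### Treatment-emergent AEs are tabulated under the randomised dose, with no rule for subjects dosed from a kit that was not theirs, so after a cross-dose error an acute ocular AE can appear under the wrong dose

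*SAP*

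**What the plan says.** The attribution rule is in SAP 7.8.1: events from first intake to 7 days after last intake are treatment-emergent and will "be assigned to the randomised treatment". The primary endpoint follows this rule. SAP 7.4 states that "The assessment of ocular adverse events will be done on treated set" and refers to 7.8.1 "for a description of the analysis of adverse events". SAP 7.5.2 does the same for drug-related AEs, a secondary endpoint.

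SAP 6.2, Table 6.2: 1, lists two administration errors as important protocol violations:

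- C2.1: "Trial medication administered on any of days 2-13 was not from the medication kit assigned to subject". It leads to exclusion from no analysis set.
- C2.2: "Subject was administered medication from kit assigned to another subject on days 1 or 14 (PK visit". It leads to exclusion from the pharmacokinetic set only.

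Both kinds of subject stay in the treated set, which SAP 6.3 defines without regard to which dose was taken: "This subject set includes all subjects who were documented to have been administered at least one dose of investigational treatment".

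The randomised contrast is between the two doses. Under Protocol 4.1.2 subjects are "assigned at random in a 1:1 ratio of 25 and 100 mg dose per group".

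**The concern.** The trial's main purpose is to describe ocular safety at two doses. Protocol 1.2.3 and 2.1 describe the visual effects as arising soon after intake, mostly gone within an hour, and closely linked to peak plasma concentration. For such events the dose taken that day is the relevant exposure. Protocol 1.2.4 reports no departure from dose proportionality between 25 and 100 mg in the multiple-dose trial, so a kit error across doses would mean roughly a four-fold difference in exposure (100/25 = 4).

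The SAP recognises kit errors and acts on them for pharmacokinetics, but says nothing about them for the primary safety endpoint. An eye AE that follows 100 mg in a subject randomised to 25 mg would be reported in the 25 mg column. This raises the low-dose percentage and shrinks the apparent difference between doses. The extent-of-exposure summary in SAP 7.7 would not reveal it, because exposure is computed from start and stop dates alone.

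**Working it through.** The plan states no figure that depends on this rule, so the check is mainly of text, followed by the size of the effect.

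**Text.** I looked for any rule that uses the dose actually taken in SAP 6.1, 6.3, 7.4, 7.7 and 7.8 and in Protocol 7.3.1 and 7.3.3. None gives one, and none asks for a sensitivity table or listing of subjects with kit errors.

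**Inputs.** Allocation is 1:1 (Protocol 4.1.2). Cell size comes from Protocol 7.6: "The size of 10 subjects per population and per dose group is in general considered as sufficient". The planned total follows: 3 populations × 2 doses × 10 = 60, as stated there. Each dose column has 3 × 10 = 30. The number of kit errors is not given and has to be assumed.

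**Chance that a swapped kit holds the other dose.** With m kits of each dose, and the wrong kit drawn at random from the other subjects' kits, the chance is m/(2m − 1).

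- Same population of 20 (m = 10): 10/19 = 52.6%
- Any of the other 59 kits (m = 30): 30/59 = 50.8%

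**Effect of moving one subject with an event.** Let each dose group have n subjects, with k events in the giving group and j in the receiving group.

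- Giving group: k/n becomes (k − 1)/(n − 1), a fall of (n − k)/[n(n − 1)]. This is largest at k = 1, where it equals 1/n.
- Receiving group: j/n becomes (j + 1)/(n + 1), a rise of (n − j)/[n(n + 1)]. This is largest at j = 0, where it equals 1/(n + 1).

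| Group size | Giving, at most | Receiving, at most |
|---|---|---|
| Cell, n = 10 | 1/10 = 10.0 points | 1/11 = 9.1 points |
| Dose column, n = 30 | 1/30 = 3.3 points | 1/31 = 3.2 points |

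**Assumed example, one population.** Eye AEs by randomised dose are 2/10 at 25 mg and 4/10 at 100 mg. One of the two 25 mg subjects with an event had in fact been dosed from a 100 mg kit throughout.

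- As randomised: 20.0% vs 40.0%, a difference of 20.0 points
- By dose received: 1/9 = 11.1% vs 5/11 = 45.5%, a difference of 34.3 points

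**Duration of the error.** C2.2 concerns day 1 or day 14, and C2.1 any of days 2 to 13. A one-day error leaves 13 of 14 days on the randomised dose. Under a most-days rule that subject's column does not change, so the tables are corrected only for a sustained error. A brief error can be made visible only in a listing.

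**The case against.** The strongest case against is that this is a minor clarification. Kits are subject-specific (Protocol 4.1.6) and intake is supervised (Protocol 4.3 and 6.2.2), so C2 errors should be rare, and about half would not change the dose. The 7.8.1 sentence mainly separates study periods. Detailed AE handling is deferred to an internal guideline, deviations are judged at the blinded report planning meeting, and no hypothesis is tested. AEs are counted by subject, so someone who also had an eye AE on the randomised dose is still correctly counted there. Removing C2.2 subjects from the pharmacokinetic set proves little about AEs, since a wrong kit directly invalidates that day's concentrations.

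Most of this limits the size of the point but does not remove it. The SAP text names the randomised treatment explicitly. The guideline cannot be read and cannot be assumed to override that wording. The planning meeting is blinded, and no reassignment by dose taken is described.

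A reader might infer four stronger things that the documents do not support:

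- **That numbered lists for six subject groups (Protocol 4.1.2) make this error likely.** A kit taken out of order or from the wrong group is code C1. The number given is itself the allocation and is recorded, so recorded and taken dose still agree. Only C2 separates them.
- **That one moved subject shifts both cells by 10 points.** The denominators change as well, so the receiving cell moves by at most 9.1.
- **That dose taken can be read straight from the eCRF.** Protocol 4.1.2 and 7.5 say it holds the assigned medication number. Protocol 4.1.4 and SAP 7.3 add only date and time of intake.
- **That every endpoint other than pharmacokinetics is a safety endpoint.** The further-endpoint sections are not visible, so this cannot be checked.

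**Conclusion.** The point holds in a contingent form. The plan tabulates all treatment-emergent AEs, the primary ocular AEs included, under the randomised dose. It foresees dosing from a kit that was not the subject's own, and has no rule or listing for the resulting safety data. After a cross-dose error, an acute ocular AE can stand under a dose other than the one that preceded it.

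The size rests on an assumed single misplaced subject with an event: at most 10.0 and 9.1 points in the two cells of 10, and about 3 points in each dose column of 30. The figure of about one half for swaps that cross doses assumes the wrong kit is drawn at random. The documents give no frequency for C2 errors and no evidence that one occurred, so this is a gap in the rule and not a demonstrated bias. It is worth closing because the trial is small, the events are acute, and comparison by dose is central.

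**What to change.** In SAP 6.1 and 7.8.1, state that AEs and other safety data are tabulated by the dose actually received. For subjects who took both doses, fix the column rule before unblinding, for example the dose taken on most days.

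Add a listing of all C2.1 and C2.2 subjects that shows the randomised dose, the dose taken on each affected day, and any AE that started after a wrong-kit dose. The listing is essential, because the most-days rule leaves brief errors where they were.

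The cost is the revised SAP text, one derived variable and one listing. The derivation should use whatever records identify C2 violations, such as the drug accountability records in Protocol 4.1.8, so it takes somewhat more work than reading a field from the eCRF. Protocol 7.3.1 and 7.3.3 do not prescribe attribution by randomised dose, so a protocol amendment does not appear necessary. If no cross-dose error occurs, no result changes.

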7.8.2 Laboratory data

The analyses of laboratory data will be descriptive in nature and will be based on BI standards ([6](#)).

7.8.3 Vital signs

Descriptive statistics of vital signs (BP and PR) observed values and change from baseline will be provided for both supine and standing positions separately. Orthostatic BP and PR will also be summarized descriptively. Orthostatic changes in BP are flagged for falls in systolic blood pressure of at least 20 mm Hg or diastolic blood pressure of at least 10 mm Hg. Orthostatic changes are calculated as standing – supine.

Baseline values for vital signs will be the observations taken at Visit 2

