1.2.3 Clinical Study

Safety data from five phase I studies are available (U12-1034; U13-1182; U12-2165; U13-1303; c02098989) in healthy young and healthy elderly volunteers. In all five healthy volunteer trials, the most frequent drug related adverse events were visual side effects that occurred shortly after dosing and mostly resolved within 1 hour. Therefore they are in close connection to maximum BI 409306 plasma concentrations as the concentration-time profile sharply and steeply peak within the first 1-2 hours and then rapidly decline afterwards.

In vitro data on BI 409306 evaluating potential activity against recombinant human PDE6 isoforms in the retina revealed no relevant activity, indicating that visual disturbances do not seem to be linked to PDE6 or other off-target activity of BI 409306 (cf. Section 1.1). Two preclinical studies were then conducted to further explore this phenomenon. The first study confirmed that there was a widespread distribution of PDE9 in the rat and human retina; and the second revealed enhanced spike activity of the retinal ganglion cells and that these activities were shown to be reversible. It was concluded that PDE9 protein is expressed in retina and PDE9- inhibition leads to changes in retina physiology that likely result in the transient visual effects noted in human.

Overall, there were no relevant changes observed for laboratory, ECG recordings, and vital signs following treatment with BI 409306 when compared to placebo. Only a rapid and short lasting increase in supine pulse rate of 12.9 ± 4.4 bpm was detected in Chinese CYP2C19 poor metabolizers subjects treated with BI 409306 (100 mg single dose) in Study 1289.4 (c02098989). Following this observation, pharmacometric analysis of all available human data revealed a BI 409306 plasma concentration dependent increase in supine pulse reaching a maximum of 7-13 bpm (median) at high exposure end in CYP2C19 poor metabolizers treated with BI 409306 at 100 mg. The maximum effects of BI 409306 on pulse rate were generally achieved at maximum BI 409306 plasma concentrations (20-30 minutes post dose) and disappeared rapidly with declining concentrations.

None of the safety data presented a safety issue for further clinical trials.

Doc. No.: c02218444-07 Trial Protocol Revision 3 Page 20 of 101

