Single dose of 100 mg BI 409306 in Chinese CYP2C19 poor metabolizers subjects showed a rapid and short lasting increase in supine pulse rate of 12.9 ± 4.4 bpm. Further observations on this population revealed a BI 409306 plasma concentration dependent increase in supine pulse reaching a maximum of 7-13 bpm (median) at high exposure (median C_{max} was achieved at 0.417 h) approximately 25 min minutes post dose in Trial 1289.4 and ranged from 0.167 to 0.750 h post dose) and disappeared rapidly with declining concentrations (c02098989). This study will include 24-hour heart rate monitoring to further explore the cardiac safety of BI 409306.

The ophthalmologic physiology and neurophysiological biomarkers observations, along with the additional safety and pharmacokinetic profiles will support further studies to define safety and efficacy of BI 409306 in patients with AD and CIAS.

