3.2 DISCUSSION OF TRIAL DESIGN, INCLUDING THE CHOICE OF CONTROL GROUP

This randomised, double-blinded, parallel group design was chosen for this study to observe the effects of BI 409306 within the patient groups (AD, CIAS) and healthy volunteers for two treatments. Each eligible patient or healthy volunteer will be blindly randomized to either the BI 409306 25 mg or 100 mg dose treatment. The patient or healthy volunteer will be dispensed three tablets from the study medication carton assigned. If randomized to the 25 mg dose group, they will be taking one BI 409306 25 mg and two BI 409306 50 mg matching placebo tablets; or to the 100 mg dose group, one BI 409306 25 mg matching placebo and two BI 409306 50 mg tablets.

The population/patient group sizes (20 subjects with 10 per dose group) are in general considered sufficient for the exploratory nature of this study.

Doc. No.: c02218444-07

Page 27 of 101

The healthy volunteer group acts as the control, with double blinding to provide additional control. Refer to Section 3.3.2 for description of age-comparable healthy volunteers.

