7.8.5 Others

24-hour Holter Monitoring

The 24-hour Holter monitoring will be analyzed using descriptive statistics.

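### For Day 1 post-dose pulse, the visible SAP names no 100 mg minus 25 mg difference with an interval, assigns no display layout, and takes change from Visit 2 rather than from the Day 1 pre-dose value

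*SAP*

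**What the plan says.** Protocol 1.2.3 reports no relevant vital-sign changes in earlier studies, with one exception: "Only a rapid and short lasting increase in supine pulse rate of 12.9 ± 4.4 bpm was detected in Chinese CYP2C19 poor metabolizers subjects" after a single 100 mg dose. It adds that the rise depends on plasma concentration, reaches a median maximum of 7 to 13 bpm at high exposure, peaks 20 to 30 minutes after dosing and fades quickly.

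Protocol 5.2.6 therefore adds, on Day 1 only, supine pulse before the dose and at 20, 30, 45 and 90 minutes after it.

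There is no placebo arm (Protocol 3.2): "Each eligible patient or healthy volunteer will be blindly randomized to either the BI 409306 25 mg or 100 mg dose treatment". Placebo tablets serve only to keep the two doses looking alike. Under Protocol 4.1.2, subjects are "assigned at random in a 1:1 ratio of 25 and 100 mg dose per group".

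The analysis in SAP 7.8.3 is: "Descriptive statistics of vital signs (BP and PR) observed values and change from baseline will be provided for both supine and standing positions separately". The same section fixes the vital-signs baseline at Visit 2. SAP 6.1 defines, among other layouts, a 7-column display (population by dose, plus total) and a 3-column display (dose, plus total). The visible text assigns neither to vital signs. Protocol 7.2 and SAP 7 rule out hypothesis testing.

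**The concern.** The timed Day 1 series was added because of a specific, short-lived signal. With all subjects on active drug, the change within a group mixes any drug effect with whatever else happens that morning: time of day, settling into the clinic, repeated sampling and, for in-patients, a meal scheduled 1 hour (±1 hour) after dosing (Protocol 4.1.4). Taking the change from Visit 2 adds day-to-day variation, although a pre-dose value is collected on Day 1 itself.

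These influences act on both doses alike. The 100 mg minus 25 mg difference, which rests on randomisation, removes them in expectation. If it is not specified, a reader must form it by eye from the tables, without an interval and possibly from six cells of 10. The cardiac question that prompted the extra measurements would then have no pre-specified estimate.

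**Working it through.** **Planned numbers.** Protocol 7.6: "The size of 10 subjects per population and per dose group is in general considered as sufficient". So 3 populations × 2 doses × 10 = 60, and 3 × 10 = 30 per dose, which matches the protocol's totals. The sample size is expressly not based on power, so there is no power figure to reproduce.

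**SD.** The documents give no SD for pulse change in this trial. The only figure is the ± 4.4 bpm above. I read it as an SD, which is an assumption, and show larger values because it comes from poor metabolisers after one dose.

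**Formula.** SE of the dose difference = SD × √(2/n), with n per dose. The 95% half-width = t(0.975, df) × SE.

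- One population: n = 10, df = 18, t = 2.101, SE = 0.447 × SD.
- Pooled and stratified by population: n = 30, df = 60 − 6 = 54, t = 2.005, SE = 0.258 × SD.
- SE ratio: 0.447/0.258 = √3 = 1.73.
- Half-width ratio: 1.73 × 2.101/2.005 = 1.82 (1.815 before rounding).

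| Assumed SD (bpm) | One population, 10 vs 10 | Pooled, 30 vs 30 |
|---|---|---|
| 4.4 | ±4.1 | ±2.3 |
| 7 | ±6.6 | ±3.6 |
| 10 | ±9.4 | ±5.2 |

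For SD 7: 7 × 0.447 × 2.101 = 6.6 and 7 × 0.258 × 2.005 = 3.6.

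**Against the 3-column display.** If the two dose columns are used, the pooled difference can be read off, and the 1.8 does not apply. What is then missing is the interval and the adjustment. If population explains a share f of the total variance, ignoring it widens the pooled interval by about 1/√(1 − f): 1.05 for f = 0.10 and 1.41 for f = 0.50 (f is assumed). The single-population interval is then about 1.72 down to 1.29 times the unstratified pooled one.

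**Baseline as covariate.** Compared with a plain change score, the half-width is multiplied by about √((1 + r)/2), where r is the correlation between pre-dose and post-dose pulse. For assumed r = 0.5 this is 0.87, and for r = 0.7 it is 0.92.

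**Which baseline.** Three texts differ:

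- SAP 7.8.3 uses Visit 2, which the flow chart places on Day −2 to −1.
- SAP 6.7 uses the last value before first intake, unless otherwise specified.
- Protocol 5.2.6 calls the Day 1 pre-dose orthostatic measurement the baseline, and also collects a Day 1 pre-dose supine pulse.

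As written, SAP 7.8.3 overrides the default, so the Day 1 change would not start from the Day 1 pre-dose value.

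**The case against.** The trial is an exploratory Phase Ic study, declared descriptive throughout. Its primary objective is ocular, and pulse is neither a primary nor a secondary endpoint. This limits how much weight the point can carry. It does not remove it, because an estimate with an interval and no p-value is not a hypothesis test.

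A reader might infer that the dose difference will never be produced. The documents do not support that. SAP 6.4 and 7.6 and the pages between the references and the history table are not public, so the most that can be said is that the visible text does not specify it. Nor does the SAP commit the reader to cells of 10, since the by-dose display may be the one used, with N, mean and SD shown.

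The case against within-group change should not be overstated either. Protocol 5.2.6 has each pulse taken supine after rest and before the corresponding blood draw, and the in-patient meal nominally follows the first three readings. Time of day, earlier draws, the 90-minute reading and the Visit 2 baseline remain.

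It is tempting to extend the point to the Holter. Protocol 2.1 says "This study will include 24-hour heart rate monitoring to further explore the cardiac safety of BI 409306", and SAP 7.8.5 says only "The 24-hour Holter monitoring will be analyzed using descriptive statistics". But the Day 3 heart-rate variable is not defined in the visible text. If it is a 24-hour mean, an assumed 10 bpm rise lasting one hour moves it by 10/24 = 0.4 bpm. A precise, near-null contrast could reassure falsely, so I do not ask for one.

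**Conclusion.** The point holds for Day 1 post-dose pulse. The visible SAP gives no dose contrast, no interval, no assigned layout and a baseline that bypasses the Day 1 pre-dose value. If the effect is read within single populations, the 95% CI is about 1.8 times wider than a pooled, stratified one (SE 1.73 times larger). That assumes a common SD, a common dose effect in the three populations and full enrolment. Under the contingency in Protocol 7.3.4 (CIAS and their 10 healthy volunteers analysed alone, 15 per dose), the ratio falls to about 1.25. Against the by-dose display, the gain is the interval and the adjustment only.

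Two limits apply. The contrast is an increment between active doses; it gives neither the effect of 25 mg nor the absolute effect of 100 mg. And calling it unconfounded depends on true randomisation: Protocol 4.1 describes alternating assignment, while 4.1.2 and 7.5 describe random allocation. The primary endpoint is unaffected.

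**What to change.** In SAP 7.8.3:

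- For Day 1 supine pulse at 20, 30, 45 and 90 minutes, add the adjusted mean difference, 100 mg minus 25 mg, with a 95% CI and no p-value. Use a linear model with dose, population (AD, CIAS, HV) and the Day 1 pre-dose supine pulse as covariate.
- Name that pre-dose value as the baseline for this series, and reconcile SAP 7.8.3 with SAP 6.7 and Protocol 5.2.6.
- State which SAP 6.1 display vital signs will use, and keep the population-by-dose tables.

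Separately, reconcile the assignment wording in Protocol 4.1 with 4.1.2 and 7.5.

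The cost is a few sentences and one small table from data already collected. The small downside is that the model assumes a similar dose difference across populations, which the by-cell tables can check, though only roughly with 10 per cell. The no-testing rule is unchanged.
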